# 8.4.2 Follow-up of AEs and SAEs

Any AEs that are unresolved at the participant's last AE assessment in the study are followed up by the Investigator for as long as medically indicated, but without further recording in the eCRF. AstraZeneca retains the right to request additional information for any participant with ongoing AE(s)/SAE(s) at the end of the study, if judged necessary.

#### Clinical Study Protocol -5.0 Selumetinib - D1346C00004 Adverse Event Variables

The following variables will be collected for each AE:

- The AE (verbatim)
- The date and time when the AE started and stopped
- The CTCAE grade/max CTCAE grade/changes in CTCAE grade
- Whether the AE is serious or not (Appendix B)
- Investigator causality rating against the Investigational Product (yes or no)
- Action taken with regard to Investigational Product
- If the AE caused participant's withdrawal from study (yes or no)
- Administration of treatment for the AE
- Outcome

In addition, the following variables will be collected for SAEs:

- Date AE met criteria for SAE
- Date Investigator became aware of SAE
- Adverse event is serious due to
- Date of hospitalisation
- Date of discharge
- Probable cause of death
- Date of death
- Autopsy performed
- Causality assessment in relation to study procedure(s)
- Causality assessment to other medication

The grading scales found in the revised NCI CTCAE Version 5.0 will be utilised for all events with an assigned CTCAE grading. For those events without assigned CTCAE grades, the recommendation in the CTCAE criteria that converts mild, moderate, and severe events into CTCAE grades should be used. A copy of the CTCAE can be downloaded from the Cancer Therapy Evaluation Program website (http://ctep.cancer.gov).

### 8.4.3 Causality Collection

The Investigator should assess causal relationship between Investigational Product and each AE and answer 'yes' or 'no' to the question 'Do you consider that there is a reasonable possibility that the event may have been caused by the Investigational Product?'

For SAEs causal relationship should also be assessed for other medication and study procedures.Note that for SAEs that could be associated with any study procedure the causal relationship isCONFIDENTIAL AND PROPRIETARY76 of 168

A guide to the interpretation of the causality question is found in Appendix B to the CSP.

#### 8.4.4 Adverse Events Based on Signs and Symptoms

All AEs spontaneously reported by the participant or care provider or reported in response to the open question from the study site staff: **'Has the child had any health problems since the previous visit/you were last asked?'**, or revealed by observation will be collected and recorded in the eCRF. When collecting AEs, the recording of diagnoses is preferred (when possible) to recording a list of signs and symptoms. However, if a diagnosis is known and there are other signs or symptoms that are not generally part of the diagnosis, the diagnosis and each sign or symptom will be recorded separately.

#### 8.4.5 Adverse Events Based on Examinations and Tests

The results from the CSP mandated laboratory tests, vital signs, physical examinations, ECGs, ECHO scans and ophthalmological examinations will be summarised in the Clinical Study Report.

Deterioration as compared to baseline in CSP-mandated laboratory tests, vital signs, ECGs, echocardiogram scans and ophthalmological examinations should therefore only be reported as AEs if they fulfil any of the SAE criteria, are the reason for discontinuation of treatment with the investigational product or are considered to be clinically relevant as judged by the Investigator (which may include but not limited to consideration as to whether treatment or non-planned visits were required or other action was taken with the study intervention, eg, dose adjustment or drug interruption).

If deterioration in a laboratory value/vital sign/ECG/ECHO is associated with clinical signs and symptoms, the sign or symptom will be reported as an AE and the associated laboratory result/vital sign/ECG/ECHO will be considered as additional information. Wherever possible the reporting Investigator uses the clinical, rather than the laboratory term (eg, anaemia versus low haemoglobin value). In the absence of clinical signs or symptoms, clinically relevant deteriorations in non-mandated parameters should be reported as AE(s).

Deterioration of a laboratory value, which is unequivocally due to disease progression, should not be reported as an AE/SAE.

Any new or aggravated clinically relevant abnormal medical finding at a physical examination as compared with the baseline assessment will be reported as an AE unless unequivocally related to the disease under study.

### 8.4.6 Hy's Law

Cases where a participant shows elevations in liver biochemistry may require further evaluation and occurrences of AST or ALT  $\ge$  3 × ULN together with TBL  $\ge$  2 × ULN may need to be reported as SAEs. Please refer to Appendix D for further instruction on cases of increases in liver biochemistry and evaluation of HL.

CONFIDENTIAL AND PROPRIETARY 77 of 168

### Clinical Study Protocol -5.0 Selumetinib - D1346C00004

### 8.4.7 Disease Progression

Disease progression can be considered as a worsening of a participant's condition attributable to the disease for which the study intervention is being studied. It may be an increase in the severity of the disease under study and/or increases in the symptoms of the disease. The development of new symptoms, or the progression of existing symptoms, of NF1-PN should be considered as disease progression and not an AE. Events which are unequivocally due to disease progression should not be reported as an AE during the study.

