# 8.4.8 Disease under Study

Symptoms of disease under study are those which might be expected to occur as a direct result of NF1-PN. Events which are unequivocally due to disease under study should not be reported as an AE during the study unless they meet SAE criteria or lead to discontinuation of the study intervention.

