# 8.4.9 Reporting of Serious Adverse Events

All SAEs must be reported, whether or not considered causally related to the study intervention, or to the study procedure(s). All SAEs will be recorded in the eCRF.

If any SAE occurs in the course of the study, Investigators or other site personnel will inform the appropriate AstraZeneca representatives within one day i.e., immediately but **no later than 24 hours** of when he or she becomes aware of it.

The designated AstraZeneca representative will work with the Investigator to ensure that all the necessary information is provided to the AstraZeneca Patient Safety data entry site within **one calendar day** of initial receipt for fatal and life-threatening events **and within 5 calendar days** of initial receipt for all other SAEs.

For fatal or life-threatening AEs where important or relevant information is missing, active followup will be undertaken immediately. Investigators or other site personnel will inform AstraZeneca representatives of any follow-up information on a previously reported SAE within one calendar day, i.e., immediately but **no later than 24 hours** of when he or she becomes aware of it.

Once the Investigators or other site personnel indicate an AE is serious in the EDC system, an automated email alert is sent to the designated AstraZeneca representative.

If the EDC system is not available, then the Investigator or other study site staff reports a SAE to the appropriate AstraZeneca representative by telephone followed by completion of a paper SAE form.

The AstraZeneca representative will advise the Investigator/study site staff how to proceed.

For further guidance on the definition of a SAE, see Appendix B of the CSP.

The reference document for definition of expectedness/listedness is the Investigator's Brochure for

In the European Union, the Sponsor will comply with safety reporting requirements and procedures as de-scribed in the European Clinical Trials Regulation (EU) No 536/2014. All Suspected Unexpected Serious Adverse Reactions (SUSARs) to investigational medicinal product will be reported to the EudraVigilance database within the required regulatory timelines.

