### 8.4.13 Adverse Events of Special Interest

Adverse events of special interest are events of scientific and medical interest specific to the further understanding of the selumetinib safety profile and require close monitoring and rapid communication by the investigators to AstraZeneca. An AESI can be serious or non-serious. All AESI should be recorded in the eCRF as soon as possible, and preferably within 24 hours of occurrence. Serious AESIs will be recorded and reported as per Section 8.4.9. Adverse events of special interest based on examinations and tests should be reported in accordance with Section 8.4.5.

Adverse events of special interest are shown in Table 14.

AESI	MedDRA Preferred Terms Defining the AESIs	
Ocular toxicity	Chorioretinopathy (central serous retinopathy [CSR]); Retinal detachment; Retinal tear; Vision blurred; Visual impairment; Vitreous floaters; Photopsia; Eye disorder; Photophobia; Retinal vein occlusion (RVO); Detachment of retinal pigment epithelium (Retinal pigment epithelial detachment [RPED]).	
Hepatotoxicity	Drug-induced liver injury; ALT increased; AST increased.	
Muscular toxicity	Blood creatine phosphokinase increased; Musculoskeletal pain; Muscular weakness; Myalgia; Rhabdomyolysis; Myoglobin blood increased; Myoglobin urine present; Acute kidney injury; Myopathy.	
Cardiac toxicity	Ejection fraction decreased; Oedema peripheral; Peripheral swelling; Oedema; Left ventricular dysfunction; Ventricular dysfunction.	
Physeal dysplasia	Metaphyseal dysplasia; Multiple epiphyseal dysplasia; Arthralgia; Joint stiffness; Joint hyperextension; Gait disturbance; Short stature.	
Choking on the capsule	Choking; Retching.	

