# **B 2** Definition of Serious Adverse Events

An SAE is an AE occurring during any study phase (i.e., run-in, treatment, washout, follow-up), that fulfils one or more of the following criteria:

- Results in death
- Is immediately life-threatening
- Requires in-participant hospitalisation or prolongation of existing hospitalisation
- Results in persistent or significant disability or incapacity
- Is a congenital anomaly or birth defect
- Is an important medical event that may jeopardise the participant or may require medical treatment to prevent one of the outcomes listed above.

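### Protocol 8.4.7 and 8.4.8 give opposite instructions for serious or treatment-ending events due to the plexiform neurofibroma, so whether these count as AEs or SAEs depends on which section a site follows

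*Protocol*

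**What the plan says.** Protocol 8.4.7 (Disease Progression) contains two exclusions. The first concerns symptoms: "The development of new symptoms, or the progression of existing symptoms, of NF1-PN should be considered as disease progression and not an AE". The second concerns events: "Events which are unequivocally due to disease progression should not be reported as an AE during the study". Neither has an exception for seriousness or for stopping study treatment.

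Protocol 8.4.8 (Disease under Study) defines its scope as follows: "Symptoms of disease under study are those which might be expected to occur as a direct result of NF1-PN". Events unequivocally due to that disease "should not be reported as an AE during the study unless they meet SAE criteria or lead to discontinuation of the study intervention".

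Protocol 8.4.9 states: "All SAEs must be reported, whether or not considered causally related to the study intervention". Appendix B 2 begins its definition with: "An SAE is an AE occurring during any study phase".

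Protocol 8.4.13 asks for every AESI, serious or not, to be entered in the eCRF. Among the terms in its Table 14 are "Musculoskeletal pain; Muscular weakness; Myalgia".

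Protocol Section 3 (Table 5) places seriousness, death, AEs leading to discontinuation and AESIs within the primary safety endpoint. SAP 4.6.2.2 tabulates SAEs, fatal SAEs, AEs leading to discontinuation and AESIs from the AE data. SAP 4.6.2 has no rule for events attributed to progression.

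**The concern.** Two adjacent sections cover the same kind of event and instruct sites differently, and neither says which prevails. Serious PN events are foreseeable: inclusion criterion 2(d) itself names tracheal displacement, and bladder obstruction with hydronephrosis, as complications of a PN.

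At stake are the primary safety counts. With one arm there is no comparator in which the same inconsistency would occur. Two sites that each follow the protocol faithfully could handle identical admissions differently. Some details also hang on SAE status: the AE variables list in 8.4.2 collects the date of hospitalisation, date of death and probable cause of death as additional items for SAEs only.

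**Working it through.** No arithmetic applies and the plan states no figure to reproduce. The check is to take each kind of PN-related event through the sections in turn.

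| Event | 8.4.7 | 8.4.8 | Other rule |
|---|---|---|---|
| Serious, unequivocally due to PN worsening | Not an AE | Report | 8.4.9: report, if it counts as an SAE |
| Non-serious, unequivocally due to PN worsening, ends study treatment | Not an AE | Report | None that decides it |
| Non-serious, unequivocally due to PN worsening, treatment continues, matches a Table 14 term | Not an AE | Not an AE | 8.4.13: record |
| New or worse symptom put down to PN, attribution less than certain | Not an AE (symptom sentence) | Not excluded | Appendix B 1: general AE definition applies |

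**Rows 1 and 2: the contradiction.** The scopes overlap, since 8.4.7 covers new or worse NF1-PN symptoms and 8.4.8 covers symptoms resulting directly from NF1-PN. A worsening PN that leads to admission satisfies both, and the instructions are opposite.

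**Does 8.4.9 settle row 1?** Not clearly. Its rule applies to SAEs, and under Appendix B 2 an event must be an AE before it can be an SAE. Read literally, an event that 8.4.7 has declared not to be an AE never reaches 8.4.9. The electronic alert described in 8.4.9 likewise starts only when a site marks an AE as serious.

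**Does other text settle it?** It points both ways. Section 8.4.5 keeps laboratory deterioration that is clearly due to progression out of both AE and SAE reporting. Appendix B 3 says how to rate causality when the disease has deteriorated through lack of effect, which presumes that such events are recorded.

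**Row 3.** Here 8.4.7 and 8.4.8 agree. The tension is with 8.4.13, which has no carve-out for progression.

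**Row 4.** The word *unequivocally* governs the event sentence of 8.4.7 but not its symptom sentence. Inclusion criterion 2(d) gives pain and motor dysfunction as PN symptoms, and these can resemble Table 14 terms such as musculoskeletal pain and muscular weakness. Attribution is least certain in this row, and the exclusion asks for no certainty.

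**Direction.** For rows 1 and 2, a site following 8.4.7 leaves out events that a site following 8.4.8 includes. Mixed practice can therefore only lower the counts relative to uniform use of 8.4.8. The number of such events cannot be obtained from the documents.

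**The case against.** The strongest reply is that this is a gap of one clause and that the rest of the protocol leans towards reporting. Section 8.4.9 is emphatic, Appendix B 1 counts deterioration of a pre-existing condition as an AE, and Appendix B 3 assumes that deterioration is assessed for causality. A careful site would probably report the admission. That is a fair account of the likely intention, but none of these passages overrides 8.4.7 or states precedence.

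A second reply is that leaving out events truly due to the PN does not understate drug toxicity; only misattributed events would do that. This stands. It limits what the lower counts mean, but the endpoint counts SAEs and discontinuations whatever their cause, so the inconsistency remains.

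Several stronger readings are tempting but unsupported:

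- *That such events leave no trace.* They may be absent as AEs or SAEs. However, progression is a listed reason for stopping treatment (Protocol 7.1), SAP 4.1.1.1 tabulates reasons for discontinuation, and SAP 4.2.5.6 handles death as a progression event.
- *That the Safety Review Committee would miss them.* That committee serves the dose-finding phase, and SAP Section 4 records that the dose schema was approved at the end of it.
- *That malignant transformation would be classed as progression.* Section 8.4.7 does not mention it, and exclusion criterion 1 treats MPNST as a separate diagnosis.
- *That the AESI problem is another case of 8.4.7 against 8.4.8.* For non-serious symptoms that do not stop treatment, both exclude it.
- *That universal symptomatic entry, or the 6% with progressive disease in SPRINT, indicates the size.* Neither gives the frequency of serious PN worsening.

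**Conclusion.** The point holds as a contradiction in the protocol text. For an event that is unequivocally due to PN worsening and is serious or ends study treatment, 8.4.7 says not to report it as an AE and 8.4.8 says to report it. Neither 8.4.9 nor the SAP clearly resolves this. Counts of SAEs, fatal SAEs and AEs leading to discontinuation therefore depend on the section a site follows, with any effect in the downward direction.

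The size is unknown and cannot be derived. The conclusion rests on two assumptions: that such events occur, and that at least some sites apply 8.4.7 as written. The missing certainty threshold in the 8.4.7 symptom sentence, and its tension with 8.4.13, form a separate and lesser point. The text should be corrected; nothing here shows that the safety results are materially wrong.

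**What to change.** Reconcile 8.4.7 with 8.4.8, 8.4.9 and 8.4.13:

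- Add to 8.4.7 the exception already in 8.4.8: "unless they meet SAE criteria or lead to discontinuation of the study intervention".
- Apply *unequivocally* to the symptom sentence of 8.4.7 as well as to its event sentence.
- State how 8.4.7 and 8.4.13 fit together when a PN symptom matches an AESI term. A rule to record every Table 14 term even when it is due to the PN is not proposed. It would add disease symptoms to the AESI counts, and SAP 4.6.2.2 lists no AESI table restricted to related events.
- Check progression cases already on file, so that those meeting the exception are handled alike at all sites.

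The cost is protocol wording, a site memo, the check of existing cases and a few more AE or SAE records, some of them judged unrelated.

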# 8.4.8 Disease under Study

Symptoms of disease under study are those which might be expected to occur as a direct result of NF1-PN. Events which are unequivocally due to disease under study should not be reported as an AE during the study unless they meet SAE criteria or lead to discontinuation of the study intervention.

# 8.4.9 Reporting of Serious Adverse Events

All SAEs must be reported, whether or not considered causally related to the study intervention, or to the study procedure(s). All SAEs will be recorded in the eCRF.

If any SAE occurs in the course of the study, Investigators or other site personnel will inform the appropriate AstraZeneca representatives within one day i.e., immediately but **no later than 24 hours** of when he or she becomes aware of it.

The designated AstraZeneca representative will work with the Investigator to ensure that all the necessary information is provided to the AstraZeneca Patient Safety data entry site within **one calendar day** of initial receipt for fatal and life-threatening events **and within 5 calendar days** of initial receipt for all other SAEs.

For fatal or life-threatening AEs where important or relevant information is missing, active followup will be undertaken immediately. Investigators or other site personnel will inform AstraZeneca representatives of any follow-up information on a previously reported SAE within one calendar day, i.e., immediately but **no later than 24 hours** of when he or she becomes aware of it.

Once the Investigators or other site personnel indicate an AE is serious in the EDC system, an automated email alert is sent to the designated AstraZeneca representative.

If the EDC system is not available, then the Investigator or other study site staff reports a SAE to the appropriate AstraZeneca representative by telephone followed by completion of a paper SAE form.

The AstraZeneca representative will advise the Investigator/study site staff how to proceed.

For further guidance on the definition of a SAE, see Appendix B of the CSP.

The reference document for definition of expectedness/listedness is the Investigator's Brochure for

In the European Union, the Sponsor will comply with safety reporting requirements and procedures as de-scribed in the European Clinical Trials Regulation (EU) No 536/2014. All Suspected Unexpected Serious Adverse Reactions (SUSARs) to investigational medicinal product will be reported to the EudraVigilance database within the required regulatory timelines.

### 8.4.10 Pregnancy

All pregnancies and outcomes of pregnancy should be reported to AstraZeneca except for:

• If the pregnancy is discovered before the study participant has received any study intervention.

#### 8.4.10.1 Maternal Exposure

Not applicable due to age of participants.

#### 8.4.10.2 Paternal Exposure

Not applicable due to age of participants.

### 8.4.11 Medication Error, Drug Abuse, and Drug Misuse

#### 8.4.11.1 Timelines

If an event of medication error, drug abuse, **or** drug misuse occurs during the study, then the Investigator or other site personnel informs the appropriate AstraZeneca representatives within **one calendar day**, i.e., immediately but **no later than 24 hours** of when they become aware of it.

The designated AstraZeneca representative works with the Investigator to ensure that all relevant information is completed within **one** (Initial Fatal/Life-Threatening or follow-up Fatal/Life-Threatening) **or 5** (other serious initial and follow-up) **calendar days** if there is an SAE associated with the medication error, drug abuse, or drug misuse (see Section 8.4.9) and **within 30 days** for all other events.

#### 8.4.11.2 Medication Error

For the purposes of this clinical study a medication error is an **unintended** failure or mistake in the treatment process for an IMP/study intervention or AstraZeneca NIMP that either causes harm to the participant or has the potential to cause harm to the participant.

The full definition and examples of medication error can be found in Appendix B 4.

### 8.4.11.3 Drug Abuse

Drug abuse is the persistent or sporadic **intentional**, non-therapeutic excessive use of IMP/study intervention or AstraZeneca NIMP for a perceived reward or desired non-therapeutic effect.

The full definition and examples of drug abuse can be found in Appendix B 4.

#### 8.4.11.4 Drug Misuse

Drug misuse is the **intentional** and inappropriate use (by a study participant) of IMP/study intervention or AstraZeneca NIMP for medicinal purposes outside of the authorised product information, or for unauthorised IMPs/study intervention(s) or AstraZeneca NIMPs, outside the intended use as specified in the protocol and includes deliberate administration of the product by the wrong route.

The full definition and examples of drug misuse can be found in Appendix B 4.

# 8.4.12 Medical Device Deficiencies

This section is not applicable for this study.

### 8.4.13 Adverse Events of Special Interest

Adverse events of special interest are events of scientific and medical interest specific to the further understanding of the selumetinib safety profile and require close monitoring and rapid communication by the investigators to AstraZeneca. An AESI can be serious or non-serious. All AESI should be recorded in the eCRF as soon as possible, and preferably within 24 hours of occurrence. Serious AESIs will be recorded and reported as per Section 8.4.9. Adverse events of special interest based on examinations and tests should be reported in accordance with Section 8.4.5.

Adverse events of special interest are shown in Table 14.

AESI	MedDRA Preferred Terms Defining the AESIs	
Ocular toxicity	Chorioretinopathy (central serous retinopathy [CSR]); Retinal detachment; Retinal tear; Vision blurred; Visual impairment; Vitreous floaters; Photopsia; Eye disorder; Photophobia; Retinal vein occlusion (RVO); Detachment of retinal pigment epithelium (Retinal pigment epithelial detachment [RPED]).	
Hepatotoxicity	Drug-induced liver injury; ALT increased; AST increased.	
Muscular toxicity	Blood creatine phosphokinase increased; Musculoskeletal pain; Muscular weakness; Myalgia; Rhabdomyolysis; Myoglobin blood increased; Myoglobin urine present; Acute kidney injury; Myopathy.	
Cardiac toxicity	Ejection fraction decreased; Oedema peripheral; Peripheral swelling; Oedema; Left ventricular dysfunction; Ventricular dysfunction.	
Physeal dysplasia	Metaphyseal dysplasia; Multiple epiphyseal dysplasia; Arthralgia; Joint stiffness; Joint hyperextension; Gait disturbance; Short stature.	
Choking on the capsule	Choking; Retching.	

